--	--

	
stored as a back-up. For participants who entered in the blinded version and then were unblinded and vaccinated, baseline serology will not be performed again, taking the values from the baseline visit performed at the first visit.
 

• For linking purposes, each participant will be assigned a treatment identification number. The number of each administered treatments must be recorded in the eCRF.

• Injection of study vaccine After completing all prerequisite procedures prior to injection, one dose of the assigned vaccine will be administered IM in the deltoid muscle, preferable of the non-dominant arm. If the investigator or delegate determines that the participant's health on the day of administration temporarily precludes administration, the visit will be rescheduled within 1 week. There will be a 15-minute wait after each vaccination to monitor for any rare anaphylactic reaction. At Day 56 after first vaccination, all participants will get a second injection of the investigational vaccine (Second Injection Visit)

• Safety participant contacts Every 4 Weeks for 52 weeks there will be telephone calls following vaccination. They will be used to continuously collect any SAE and MAE data. Participants can report any AE they experience at any time during the study period; however, only SAE and MAE will be entered into the eCRF. In-person visits will occur for Day 28 visit (to collect solicited and unsolicited events, Day 56 (Second Injection Visit), Day 84 and Week 24, and Week 52 visits.

• Efficacy participant contacts All participants will have efficacy participant contacts weekly, for 52 weeks following vaccination. There will be approximately 52 efficacy participant contacts. All efficacy participant contacts will be emails, although other methods such as phone calls or text messages, if preferred, are acceptable. Each participant contact needs to be recorded in the study electronic case report form. The purpose of these participant contacts is to ask if the participants had any symptoms of illness they may be experiencing, regardless of severity. Any possible COVID-19 relevant symptoms will trigger laboratory testing for SARS-CoV-2 infection.

• Illness participant contact visits (Confirmed or suspected infection during study) Participants will be provided detailed instructions regarding the signs and symptoms of COVID-19 disease at each participant contact and will be instructed to seek medical attention and notify study staff should symptoms occur. Symptoms of interest include fever, cough, difficulty breathing, diarrhea, nausea, vomiting, prolonged fatigue, respiratory symptoms, chills, myalgia, sore throat, headache, congested/runny nose, pneumonia, difficulty swallowing, anosmia/ageusia (loss of sense of smell/taste), and neurological events. During the observation period of the study, if any of these symptoms develop in a participant, he/she should immediately follow local procedures for care of suspected COVID-19 illness and contact the study team. If a COVID-19 infection is found during the study, a case investigation will be undertaken according to locally recommended procedures.

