Visit plan	
All participants will have at least 6 (six) planned in-person visits on Screening visit/First Injection Visit and Day 28, Day 56 (Second Injection Visit), Day 84, Week 24, and Week 52. The Screening/baseline visit will entail reviewing the ICF, completing a medical history of the participant, reviewing inclusion and exclusion criteria, and collecting a blood sample for HIV viral load and CD4/CD8 counts. A baseline SARS-CoV-19 antibody (Nexelis Laboratories), and a urine pregnancy test in women of child-bearing potential will be performed. The vaccine will be administered after having the negative result on the pregnancy test. Participants are required to remain at the study site for a minimum of 15 minutes after receiving the vaccine to monitor for any vaccine-related AE.
 
Participants will be given access to an e-diary or paper diary card to record solicited AE from First Injection Visit- day 7 and unsolicited AE from First Injection Visit- day 28. The data in the completed e-diary or diary card will be reviewed and data will be collected on Day 28.

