### **3.3 Sampling/Study Schedule**

All participants will have at least six planned in-person visits on First Injection Visit and Day 28, Day 56 (Second Injection Visit), Day 84, Week 24, and Week 52. The first visit, the Screening visit, will entail reviewing the ICF, completing a medical history of the participant, reviewing inclusion and exclusion criteria, collecting samples, performing HIV viral load and CD4/CD8 counts. At that visit (First Injection Visit), a urine pregnancy test in women of child-bearing potential will be performed (local site or laboratory) . The pre-vaccination blood drawn will be performed at First Injection Visit to obtain a viral load and a baseline CD4 count (CMH laboratory), a baseline SARS-CoV-19 antibody (Nexelis Laboratories), and baseline immunogenicity levels. Participants are required to remain at the study site for a minimum of 15 minutes after receiving the vaccine to monitor for any vaccine-related AE.

Participants will be given access to an e-diary or paper diary card to record solicited AE from First Injection Visit- day 7 and unsolicited AE from First Injection Visit-28. Participants will review their e-diary or diary card with study staff at their second in-person visit on Day 28. A new e-diary or paper diary card to record solicited and unsolicited AEs from Second Injection will be provided at Second Injection Visit- Day 56. The data in the completed e-diary or diary card will be reviewed and data will be collected at visit on Day 84.

Data collected from e-diaries and diary cards will be uploaded into the participant's eCRF. Further details are outlined in Section 3.7 and 5.1.

All participants will be contacted on a weekly basis by the site (or through an automated message (email) with a link to answer the questions on whether or not they had SAE, MAE or COVID-19 symptoms) to be reminded to report any signs or symptoms of illness to study staff. The

reporting and monitoring of any participant illness are consistent with meeting the primary efficacy objective. If a participant becomes ill, they will be asked to immediately proceed to the site designated by their local study team where they will be assessed and treated as deemed appropriate. Participants will also receive a telephone call every 4 weeks to evaluate for the incidence of any SAE and MAE.

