- **Check and record prior and concomitant medication/vaccines**

Prior medications and concomitant medication/injection must be checked and recorded in the eCRF. Prior medications should include any medication taken by the participant within 14 days prior to screening. Participants will be asked to avoid over-the-counter medications such as antipyretics (e.g., acetaminophen) and anti-inflammatory medications (e.g., ibuprofen, naproxen) in the 12 hours before study vaccine receipt but will be allowed to take these over-the-counter medications as needed to treat fever or other adverse events after vaccination. Usage of these over-the-counter medications will be recorded as concomitant medications and linked to the adverse event collected as solicited or unsolicited events according to the symptom.

- **Check and record intercurrent medical conditions**

Any medical conditions that have arisen are recorded in the eCRF.

- **Treatment number allocation**

The treatment number will be allocated within each step. The number of each administered treatment must be recorded in the eCRF.

- **Injection of study vaccine**

After completing all prerequisite procedures prior to the active vaccine injection, one dose of the assigned vaccine will be administered IM, in the deltoid muscle, preferable of the non-dominant arm. If the investigator or delegate determines that the participant's health on the day of administration temporarily precludes administration, the visit will be rescheduled within 1 week. There will be a 15-minute wait after each vaccination to monitor for any rare anaphylactic reaction. A second injection, of active vaccine Ad5-nCoV, will be administered to all participants on Day 56.

- **Safety participant contacts**

Every 4 weeks there will be telephone calls (Weeks 8-52) to continuously collect any SAE and MAE data. Participants can report any AE they experience at any time during the study period but only SAE and MAE will be entered into the eCRF. Safety participant contacts will occur at First Injection Visit (for 15 minutes post-vaccination), Day 28 (to collect the diary), Day 56 (Second Injection Visit), Day 84 (to collect the diary), Month 4, 5, 6, 7, 8, 9, 10, 11, and 12. Safety participant contacts will be a telephone call for Months 2, 3, 4, 5, 7, 8, 9, 10 and 11, and as an in-person visit on Month 1 (Day 28), Month 2 (Day 56), Month 3 (Day 84), Month 6 (Week 24), and Month 12 (Week 52).

- **E-diary and Diary Cards**

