### **Warnings and Precautions**

1. This vaccine is strictly prohibited to be administered by intravascular injection.
2. Epinephrine and other drugs as well as equipment should be in place when the vaccine is used, in case emergency treatment of severe allergic reactions will be needed. Those who are immunized with this vaccine should be observed for at least 30 minutes at the site.
3. As with all vaccines, this vaccine may not produce 100% protection in the vaccinated population.
4. The vaccine must be stored in the place not accessible by children.
5. The vaccine should be shaken before injection. It should not be used under following circumstances: presence of foreign objects, cracked vaccine syringe, unclear or expired label, or any other abnormal appearance of the vaccine.
6. No disinfectant in contact with the vaccine when injection.

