## **7. SAFETY**

A primary objective of this study focuses on the tolerability and safety of receiving two doses of  $5 \times 10^{10}$ vp Ad5-nCoV vaccine. This will be measured by the incidence of SAE and MAE within 52 weeks of receiving the vaccine and solicited AE (*local* injection site reactions and *general* reactions within the seven days following vaccination) and unsolicited AE within 28 days after vaccination.

The investigator or site staff is/are responsible for the detection, documentation and reporting of events meeting the criteria and definition of an AE, MAE, or SAE as provided in this protocol. Each participant will be instructed to contact the investigator immediately should they manifest any signs or symptoms they perceive as serious.

Table 3. Adverse Event Reporting:

Participants	30 min observation	First Injection Visit- Day 7	Day 8-28	Beyond day 29 until week 52
All	Post injection AE or SAE only	Solicited AEs and unsolicited AEs SAE and MAE	Any unsolicited AE only SAE and MAE	SAE and MAE only

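### The on-site wait after injection is 15 minutes in the synopsis, 3.3 and 5.1, but at least 30 minutes in the 6.1 product precaution and 30 minutes in Table 3

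*Protocol*

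**What the plan says.** The post-injection observation time is stated in seven places.

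Five give 15 minutes:
- Synopsis, study design, injection of study vaccine: "There will be a 15-minute wait after each vaccination to monitor for any rare anaphylactic reaction". Section 5.1 has the same sentence under the same item.
- Synopsis, visit plan: participants must "remain at the study site for a minimum of 15 minutes after receiving the vaccine to monitor for any vaccine-related AE".
- Section 3.3: "Participants are required to remain at the study site for a minimum of 15 minutes after receiving the vaccine".
- Section 5.1, safety participant contacts: "Safety participant contacts will occur at First Injection Visit (for 15 minutes post-vaccination").

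Two give 30 minutes:
- Section 6.1, Warnings and Precautions, item 2, straight after the sentence requiring epinephrine, other drugs and equipment for severe allergic reactions: "Those who are immunized with this vaccine should be observed for at least 30 minutes at the site".
- Section 7, Table 3 (Adverse Event Reporting), where the first column, applying to all participants, is headed "30 min observation".

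**The concern.** Staff will run the injection visits from sections 3.3 and 5.1, and those sections carry the shorter time. A site can therefore follow its visit procedure exactly and still send participants home before the observation period in the product precaution has ended. Someone who reacts at, say, 20 minutes may by then have left the place where epinephrine and equipment are kept ready.

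There is also a compliance problem. Section 14.2 asks monitors to check that the study is conducted according to the protocol. Release at 15 minutes agrees with 5.1 and departs from 6.1, so the document gives monitors no single standard. Sites may also differ from one another in what they do.

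**Working it through.** The protocol has no figure to reproduce here, and the point does not involve sample size, power or error rates. The check is a comparison of the texts.

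| Place | Time | Form | Stated purpose |
|---|---|---|---|
| Synopsis, injection of study vaccine | 15 min | flat, each vaccination | anaphylaxis |
| Synopsis, visit plan | 15 min | minimum | any vaccine-related AE |
| 3.3 | 15 min | minimum | any vaccine-related AE |
| 5.1, injection of study vaccine | 15 min | flat, each vaccination | anaphylaxis |
| 5.1, safety contacts | 15 min | flat, First Injection Visit only | safety contact |
| 6.1, Warnings and Precautions | 30 min | minimum, on site | given with the instruction on severe allergic reactions |
| 7, Table 3 | 30 min | recording window, all participants | post-injection AE or SAE |

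**Is it the same procedure?** Yes. The flat 15-minute wait is there to detect anaphylaxis. The 30-minute statement sits in the same numbered item as the preparations for severe allergic reactions. They cannot be read as two separate observation periods.

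**Can both be satisfied?** A 30-minute stay meets the two statements worded as minimums. It does not match the flat 15-minute wait in the synopsis and 5.1. In the other direction, release at 15 minutes meets all five of the shorter statements and fails 6.1.

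**Does any text set precedence?** No. The line between Tables 1 and 2 sends the reader to section 5.1 for detailed procedures. That is a cross-reference and not a precedence rule, and it leads to the shorter time.

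**Size of the gap.**
- Shortfall per injection: 30 − 15 = 15 minutes, and 15/30 = 50% of the time in 6.1.
- Added time per participant if corrected: 2 injections × 15 minutes = 30 minutes.
- Planned vaccine injections to which the rule applies: about 500 participants × 2 doses = 1,000. This counts planned injections, not injections known to be cut short.

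**Would data be lost?** Not for the defined endpoints. Section 7.1 collects solicited events daily from Day 0 to Day 7, and section 7.2 records every AE starting within 28 days of a dose. A reaction between 15 and 30 minutes would enter the data through those routes. What a 15-minute release does lose is direct observation of the second half of the first Table 3 window.

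**The case against.** The case against runs as follows. The 6.1 sentence says vaccinees should be observed, not that they must be. The list it belongs to reads like general product information: it also covers keeping the vaccine away from children and the absence of 100% protection. The contraindications just before it name immune dysfunction, which is hard to apply literally in an HIV trial. Table 3 is a reporting table and does not itself tell anyone to stay on site. Two of the five 15-minute statements are minimums that a 30-minute stay satisfies. The protocol does point sites to 5.1 for procedures. And nothing in the results depends on the matter.

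Some of this stands. The conflict is sharpest between 6.1 and the flat 15-minute statements in the synopsis and 5.1. The minimums in the visit plan and 3.3, and Table 3, are secondary evidence. The 50% figure is only the ratio of two times and says nothing about harm. It is also true that no endpoint estimate changes.

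None of it makes the two times agree. A sentence worded as should, with an explicit floor of 30 minutes, still makes 15 minutes too short. Even if the list began as product text, it stands in the current protocol as a precaution for use of this vaccine, and the trial's own safety table independently uses 30 minutes. The pointer to 5.1 makes the practical problem worse, because it steers sites to the shorter time.

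**Conclusion.** The contradiction is real and should be corrected. Where the 15-minute text is followed, on-site observation is 15 minutes (50%) shorter than the product precaution calls for, at each of two planned injections per participant.

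The consequence is confined to monitoring and treating acute reactions on site. No primary or secondary safety endpoint is defined on this window, and no estimate, analysis set or error rate is shown to be affected. The protocol gives no rate of reactions between 15 and 30 minutes, so the number of participants put at risk cannot be calculated and none is claimed. The conclusion rests only on the wording of the protocol, with no outside assumption.

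**What to change.** Change all five 15-minute statements (synopsis, injection of study vaccine and visit plan; section 3.3; both items in section 5.1) to at least 30 minutes on site after each injection, matching 6.1 and Table 3.

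In 5.1, state that this applies at Day 0 and Day 56, and at V1.B and V3.B for participants first assigned to placebo. The injection item already covers each vaccination, but the safety-contact item gives a time only for the First Injection Visit, so naming the visits removes any doubt about the second dose. Send the sites a short notice so that practice changes along with the text.

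The cost is a wording change, the notice, and 15 more minutes on site per injection, or 30 minutes per participant over two doses. No analysis needs to change.

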## 6.2. Product Oversight

### Product accountability

A product accountability log will be maintained by study staff to document the number of vials of product received and the disposition of each dose.

### Replacement doses

Replacements will be from the study stock.

### Return of Unused Products

Following verification of product accountability, all empty vials will be destroyed as per site policy. At the end of the study, all unused clinical trial vaccine material will be returned to the sponsor or disposed of according to the site's standard operating procedure.

### Dosage and administration of study products by the study nurse

A study nurse at each clinical site will be responsible for the administration of the IM vaccine into the patient's deltoid muscle. Products will be administered according to the prompts in the IWRS system.

### Contraindications to administration of the investigational product at First Injection Day

The following events constitute contraindications to administration of the study products at that point in time. If any contraindication is present at the time scheduled for injection, the participant may be injected at a later date, within the time window specified in the protocol, or withdrawn at the discretion of the investigator.

- Acute disease and/or fever at the time of administration.
- Fever is defined as temperature  $\geq 38.0^{\circ}\text{C}$ , taken orally.
- Participants with a minor illness (such as mild diarrhea, mild upper respiratory infection) without fever can be administered the product.

### Contraindications to administration of the study product at Day 56 Second Injection Day

- Acute disease and/or fever at the time of administration.
- Suspicion of COVID19 case due to symptoms.
- Fever ( $\geq 39.0^{\circ}\text{C}$ ) lasting at least 72 hs after the first injection.
- Adverse events related to the study product (severe or serious).

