The data produced from the phase II clinical trial further supported the safety and tolerability of receiving an Ad5-nCoV vaccine in healthy adults [2]. There were no SAE recorded in any of the study groups within 28 days of vaccination. Participants in both the  $1 \times 10^{11}$ vp and  $5 \times 10^{10}$  vp groups commonly reported mild to moderate adverse reactions, when solicited by study staff. Injection site pain was the most frequently reported solicited reaction; 57% of the  $1 \times 10^{11}$  vp dose and 56% of the  $5 \times 10^{10}$ vp group reported pain within 14 days of vaccination. A total of 9% of participants in the  $1 \times 10^{11}$ vp had a Grade 3 adverse reaction, which was significantly higher than those who received  $5 \times 10^{10}$  vp vaccine ( $p=0.0011$ ) or placebo ( $p=0.0004$ ). The most commonly reported Grade 3 adverse reaction was a fever; however, fevers were self-limiting. There was no difference in the incidence of unsolicited adverse reactions between the three groups.

Both doses of Ad5-nCoV vaccine administered in the phase II study induced a robust immune response to SARS-CoV-2, with overall comparable immunogenicity between the doses [2]. Beginning Day 14, RBD-specific ELISA antibody responses were detectable in both groups and peaked at 656.5 (575.2-749.2) in the  $1 \times 10^{11}$ vp group, and 571.0 (467.6- 697.3) in the  $5 \times 10^{10}$ vp group, on Day 28 post vaccination. While the placebo group showed no increase in antibodies from baseline, 96% of the  $1 \times 10^{11}$ vp group and 97% of the  $5 \times 10^{10}$ vp group demonstrated seroconversion of the RBD-specific ELISA antibodies at Day 28. There was seroconversion of neutralising antibodies in 59% and 47% of participants in the  $1 \times 10^{11}$ vp and  $5 \times 10^{10}$  vp dose groups, respectively. There was a significant positive T-cell response in both the  $1 \times 10^{11}$ vp and  $5 \times 10^{10}$ vp dose groups by Day 28, although the difference was not significant between the doses. A positive specific T-cell response, measured by IFN $\gamma$ -ELISpot, was found in 90% of the  $1 \times 10^{11}$  vp group and 88% of participants in the  $5 \times 10^{10}$  vp group. At Day 28, 95% of participants in the  $1 \times 10^{11}$  viral particles dose group and 91% of the recipients in the  $5 \times 10^{10}$  viral particles dose group showed either cellular or humoral immune responses.

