#### **4.2 Exclusion Criteria**

1. Participation in any other COVID-19 prophylactic drug trials for the duration of the study.  
*Note: Participation in COVID-19 treatment trials is allowed in the event of hospitalization due to COVID-19. The study team should be informed as soon as possible.*
2. Planned receipt of any vaccine (licensed or investigational), other than the study intervention, within 14 days before and after study vaccination.

3. Prior receipt of an investigational or licensed vaccine likely to impact on the interpretation of the trial data (e.g. Adenovirus vectored vaccines, any coronavirus or SARS vaccines).
4. Administration of immunoglobulins and/or any blood products within the three months prior to the planned administration of the vaccine candidate.
5. Any confirmed or suspected immunosuppressive or immunodeficient state (other than living with HIV, on stable treatment, and virologically suppressed for at least 6 months); asplenia; recurrent severe infections and chronic use (more than 14 days) of immunosuppressant medication within the past 6 months. Topical steroids or short-term (course lasting  $\leq$ 14 days) oral steroids are not an exclusion.
6. Active opportunistic infections or other AIDS-defining illness in the last six months.
7. History of allergic disease or reactions likely to be exacerbated by any component of Ad5-nCoV.
8. Any history of angioedema.
9. Any history of anaphylaxis to any vaccine component.
10. Pregnancy, lactation or willingness/intention to become pregnant within 90 days after receiving study vaccine.
11. Current diagnosis of or treatment for cancer (except basal cell carcinoma of the skin and cervical carcinoma in situ).
12. History of serious psychiatric condition likely to affect participation in the study.
13. Bleeding disorder (e.g. factor deficiency, coagulopathy or platelet disorder), or prior history of significant bleeding or bruising following IM injections or venepuncture.
14. Suspected or known current alcohol or drug dependency.
15. Severe and/or uncontrolled cardiovascular disease, respiratory disease, gastrointestinal disease, liver disease, renal disease, endocrine disorder and neurological illness (mild/moderate well-controlled comorbidities are allowed).
16. History of laboratory-confirmed COVID-19.
17. Continuous use of anticoagulants, such as coumarins and related anticoagulants (i.e. warfarin) or novel oral anticoagulants (i.e. apixaban, rivaroxaban, dabigatran and edoxaban).

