### **5.1 Study Intervention Descriptions**

**All participants will be subject to the following procedures:**

- Informed consent**

The signed informed consent must be obtained before study participation. At each subsequent participant contact requiring an intervention (such as collection of a blood sample), the participant's consent will be verified.

- Check inclusion and exclusion criteria**

All inclusion and exclusion criteria will be checked at the screening in-person visit and will be reviewed at the second injection visit.

- Collect demographic data and participant contact information**

Record demographic data such as date of birth, sex, gender, height, weight and race in the participant's eCRF. Current email addresses and or phone numbers will be collected for each participant. It is important to have complete and accurate contact information for each participant as the majority of participant contacts will occur electronically. Contact information may also be used to remind participants of up-coming in-person visits.

- **Medical history**

Obtain the participant's medical history by interview and/or review of the participant's medical records and record any pre-existing conditions or signs and/or symptoms present in a participant prior to the first study injection in the eCRF. This will include reviewing any health condition that may prevent the participant from enrolling in the study, such as an unstable health condition. HIV treatment, clinical status, viral loads and CD4 counts will be reviewed.

- **HIV status, viral load, CD4 and CD8 counts**

At Screening visit, HIV status will be verified based on a previous serologic result or previous detectable viral load. Viral load samples, and CD4 and CD8 counts will be collected at Screening visit, and week 24 and week 52 visits. Screening visit value will be used as reference value for comparison with further values.

- **Baseline serology**

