**Assessment of adverse events****Assessment of intensity**

The intensity of the following solicited AEs will be assessed as described:

The maximum intensity of local injection site redness/swelling will be scored as follows:

0: ≤ 20 mm

1: > 20 - ≤ 50 mm

2: > 50 - ≤ 100 mm

3: > 100 mm

The grade of fever will be scored as follows (oral temperatures\*):

1: ≥ 38.0°C (100.4°F) - ≤ 38.5°C (101.3°F)

2: > 38.5°C (101.3°F) - ≤ 39.0°C (102.2°F)

3: > 39.0°C (102.2°F) - ≤ 40.0°C (104°F)

4: > 40.0°C (104°F)

\*oral temperature=axillary temperature+0.2°C

The investigator will assess the maximum intensity that occurred over the duration of the event for all unsolicited AEs (including SAEs) recorded during the study. The assessment will be based on the investigator's clinical judgment.

The intensity should be assigned to one of the following categories:

- Grade 1 (mild) = An AE which is easily tolerated by the participant, causing minimal discomfort and not interfering with everyday activities.
- Grade 2 (moderate) = An AE which is sufficiently discomforting to interfere with normal everyday activities.
- Grade 3 (severe) = An AE which prevents normal, everyday activities
- Grade 4= An adverse event that is potentially life threatening.
- Grade 5=An AE which results in death.

An AE that is assessed as Grade 3 (severe) should not be confused with a SAE. Grade 3 is a category used for rating the intensity of an event; and both AEs and SAEs can be assessed as Grade 3. An event is defined as 'serious' when it meets one of the predefined outcomes.

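### The exclusion criteria are re-applied before dose 2 without being adapted to someone who has had dose 1, so the protocol does not settle who gets dose 2 after COVID-19 between the doses

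*Protocol*

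**What the plan says.** **Re-check before dose 2.** Section 5.1 says that the criteria checked at screening "will be reviewed at the second injection visit". Its screening-conclusion item places the eligibility decision before vaccination at both injection visits, and the synopsis also has eligibility verified before the second injection. Table 1 marks the criteria review at Visits 1 and 3. Table 2, for former placebo recipients, marks it at Visit 3.B.

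**The criteria.** Exclusion 3 in section 4.2 covers earlier vaccines likely to affect interpretation of the data, and gives adenovirus-vectored and coronavirus vaccines as examples. It has no carve-out for the study vaccine; exclusion 2, one line above, has one. Exclusion 16 reads "History of laboratory-confirmed COVID-19", with no time limit.

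**The Day 56 list.** Section 6.2 has a separate list of contraindications for the second injection. On COVID-19 it names only "Suspicion of COVID19 case due to symptoms". It also lists a fever of 39.0 °C or more "lasting at least 72 hs after the first injection", and "Adverse events related to the study product (severe or serious").

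**The schedule.** Sections 3.1, 5.1 and 6.1 plan dose 2 for all participants.

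**Intensity.** Section 7.2 scores fever by number: "3: > 39.0°C (102.2°F) - ≤ 40.0°C (104°F"). The word severe appears in the scale that follows: "Grade 3 (severe) = An AE which prevents normal, everyday activities".

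**The concern.** The protocol has two gates before dose 2: the eligibility re-check and the Day 56 contraindication list. They treat COVID-19 differently, and one of them cannot be applied literally at all. A site that works from the Day 56 list and a site that re-applies section 4.2 can reach opposite decisions about the same participant.

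Three things depend on that decision:

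- **Exposure.** It settles whether a participant infected between doses is injected again.
- **Per-protocol set.** Section 9.2.1 requires the correct number of doses. Whether a participant withheld at Day 56 meets that, or whether one injected despite exclusion 16 is a deviation, depends on which text governs.
- **Two-dose data.** Section 9.3.4 compares one with two doses, and Day 84 is the first sample after dose 2. Infection can itself raise S-RBD antibody. If sites differ on whether recovered cases get dose 2, the mix of participants behind the Day 84, Week 24 and Week 52 results differs by site for a reason unrelated to the vaccine.

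**Working it through.** No stated figure is to be reproduced here: section 9.1 sets no statistically derived sample size, and nothing in this point rests on power or error rate. The check is to run each participant type through both gates.

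**1. Eligibility re-check against the Day 56 list**

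| Participant at Day 56 | Section 4.2 re-applied literally | Section 6.2 Day 56 list | Schedule |
|---|---|---|---|
| Uneventful course after dose 1 | Barred by exclusion 3 | Not barred | Dose 2 |
| PCR-confirmed COVID-19 after dose 1, recovered | Barred by exclusions 3 and 16 | Not barred | Dose 2 |
| Symptoms suggesting COVID-19 now, unconfirmed | Barred by exclusion 3; exclusion 16 not met | Barred | Dose 2 |

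By Day 56 every participant has had Ad5-nCoV, an adenovirus-vectored coronavirus vaccine, so literal use of exclusion 3 bars 500 of 500. That cannot be meant. Some exclusions must therefore not carry over, but the protocol does not say which. For row 2 the answer turns entirely on whether exclusion 16 is one that does.

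**2. Former placebo recipients**

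Table 2, as tabulated, marks the criteria review at Visit 3.B but not at Visit 1.B, the visit of their first vaccine dose. Someone infected during the blinded phase could thus meet exclusion 16 for the first time at dose 2.

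**3. Fever criteria within the Day 56 list**

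Take criterion F as temperature ≥ 39.0 °C for ≥ 72 h, and criterion S as related and severe, reading a fever score of 3 or more as severe.

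| Fever after dose 1 | Score | F | S |
|---|---|---|---|
| 39.5 °C, 24 or 48 h, related | 3 | no | yes |
| 39.5 °C, 72 h, related | 3 | yes | yes |
| 39.5 °C, 72 h, unrelated | 3 | yes | no |
| 39.0 °C exactly, 72 h, related | 2 | yes | no |

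Either criterion alone bars the injection, so the list gives one answer once it is known whether a score of 3 is severe. If it is not, the first row changes from barred to not barred. The boundaries also differ: the list starts at 39.0 °C, while score 3 starts above it.

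**4. Size**

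The protocol gives no infection rate for the eight weeks between doses. As an assumption only, if 0.5% of 500 were infected and recovered in that time, 500 × 0.005 = 2.5 would be expected, and the chance of at least one is 1 − 0.995^500 = 0.918. At 1%, 5 would be expected and the chance is 0.993. This shows only that the case is likely to arise even at a low rate; it does not estimate how often.

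**The case against.** **The two gates are simply cumulative.** Table 1 has separate Day 56 marks for the criteria review and the contraindication check. Both are done, and failing either stops the injection. On that reading exclusion 16 applies and a gap in the Day 56 list permits nothing. This is a fair reading, but the protocol does not state it, and applied consistently it lets exclusion 3 stop the trial's second dose. The glossary also defines eligibility as qualification for enrolment. That supports the opposite reading, in which exclusion 16 looks back only to entry. Both readings are reasonable and they give opposite answers.

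**No site would use exclusion 3 against the study vaccine.** Agreed. The schedule is explicit, and the first study dose is hardly a foreign vaccine confusing the data. Exclusion 3 will not stop anyone. Its importance is that it proves the re-check cannot be literal and leaves the selection of exclusions to each site.

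**Some affected participants may leave the according-to-protocol immunogenicity cohort anyway.** Section 6.2 allows elimination for an intercurrent condition that can alter immune response. That could soften the effect on one analysis set. It is optional, does not name COVID-19, and does not settle the injection decision.

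**Stronger readings to avoid.** A reader might infer that the Day 56 list contradicts the fever scale. It does not: section 7.2 grades intensity and contains no dosing rule, and missing one contraindication is no permission when another is met. Nor is the 72-hour criterion redundant, since it also catches prolonged fevers judged unrelated. What remains is whether a score of 3 is severe. The label stands in the scale introduced for unsolicited events, yet section 9.3.3 grades all events as mild, moderate or severe, and section 1.2 itself speaks of severe fever.

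A reader might also be drawn by "The most commonly reported Grade 3 adverse reaction was a fever" to count many participants with disputed fevers. That sentence follows the 9% reported at 1×10^11 vp, twice this trial's dose. With 508 participants at 2:1:1 (254, 127, 127), 9% is about 23 of 254. Fisher's exact test against 1 of 127 gives p = 0.0012 and against 2 of 127 gives p = 0.004, so the reported p = 0.0011 points to roughly 1 of 127 (0.8%, exact 95% interval 0.02% to 4.3%) with any Grade 3 reaction at this dose, in healthy adults. Group sizes and counts here are inferred, so this is approximate.

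**Conclusion.** The point holds for eligibility. Sections 4.2, 5.1 and 6.2 and Tables 1 and 2 do not say together who may receive dose 2: re-applied literally, exclusion 3 bars everyone, and exclusion 16 bars recovered confirmed cases whom the Day 56 list does not bar. This is a stated rule that fails as written, not a detail left to the analysis plan.

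It should be fixed, but the documents do not support calling it a critical defect. The exclusion 3 reading has no practical victim, and the real disagreement is confined to participants with confirmed COVID-19 before Day 56. Their number cannot be derived from the protocol, and no count of affected participants should be quoted.

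The fever criteria are a minor ambiguity about one word and one boundary. The conclusion assumes that the Table 2 marks were read from the PDF correctly; the main point does not depend on them.

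**What to change.** Reconcile sections 4.2, 5.1 and 6.2, Tables 1 and 2, and the matching synopsis text:

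- List by number the exclusion criteria that are re-applied at the Second Injection Visit.
- Word exclusion 3 so that it does not count the study vaccine's own first dose, as the schedule already implies and as exclusion 2 already does for its own purpose.
- State one rule for laboratory-confirmed COVID-19 between doses, in the same words in the criteria and in the Day 56 list. Make clear how it applies to former placebo recipients at Visits 1.B and 3.B. The sponsor's clinicians choose the rule.
- Align the unconditional dose-2 wording in section 5.1 with those conditions.
- Say whether a fever score of 3 in section 7.2 counts as severe in the Day 56 list, and reconcile the two temperature boundaries. This choice is also clinical.
- Where dose 2 is withheld, record the criterion used on the existing Product Administration screen, where section 8.2 already provides a free-text reason.

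The cost is a wording amendment and a site memo. No visits, samples or procedures are added. Decisions already taken at Day 56 should be listed with the criterion applied, so that per-protocol status can be assigned consistently.
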